8.3 Subject Disposition

Subject disposition summaries will include the number of subjects who received study medication, the number of subjects who completed the study, and the reasons for study discontinuation. The number of subjects included in the safety, efficacy, and SA analyses, respectively, will be presented.

8.4 Protocol Deviations

Protocol deviations will be listed.

8.5 Demographic and Baseline Characteristics

The following key demographic and baseline factors will be summarized descriptively for the Full Analysis Set:

- Gender
- Age

- Ethnicity/Race
- Age at diagnosis
- Age at start of treatment
- Height (cm)
- Weight (kg)

8.6 Disease Characteristics and Medical History

Disease characteristics and medical history of GNEM including GNEM symptoms, adaptations, assisted devices, orthotics, medications, and treatment history will be summarized for the Full Analysis Set.

8.7 Extent of Exposure

The total number of doses administered, the total dose administered, and the total treatment duration will be summarized for the Safety Analysis Set.

Dosing compliance will also be summarized for the Safety Analysis Set. The compliance for each subject is defined as:

$$\text{Compliance} = \text{Total Dose Received} / \text{Total Dose Planned} * 100\%.$$

8.8 Efficacy Analyses

For each efficacy endpoint, summary statistics will be reported at each visit for the observed measures and their respective changes from baseline.

The efficacy endpoints measured over time will be analyzed using GEE using the Full Analysis Set. Changes from baseline will be the dependent variable, and baseline, visit will be the independent variables in the model. All efficacy endpoints were assessed at Baseline, Week 12, Week 24, Week 36, and Week 48.

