#### 7.6.4 Efficacy Analysis

Baseline values for each endpoint will be defined as the last scheduled data collection visit before beginning treatment according to the Schedule of Events ([Table 2.1](#)). Dynamometry will be administered at the Screening visit to determine eligibility and introduce subjects to performance testing to minimize training effects and will not be used for analysis purposes.

Efficacy analyses will be based on the Full Analysis Set. Generalized estimating equation (GEE) analysis will be performed to assess the changes from baseline of all efficacy endpoints with repeated measurements. Baseline will be included as a covariate in the model.

The statistical analyses will be reported using summary tables, figures, and data listings. Statistical tests will be 2-sided at the alpha =0.05 significance level. All analyses and tabulations will be performed using SAS®. Continuous variables will be summarized with means, standard deviations, medians, minimums, and maximums. Categorical variables will be summarized by counts and by percentages of subjects in corresponding categories. The final analysis will be conducted at Week 48.

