3 STUDY DESIGN

UX001-CL203 is an open-label, multicenter study to assess the safety of Ace-ER in GNEM patients with severe ambulatory impairment. Efficacy will also be assessed as a secondary objective. Approximately 45 subjects will be enrolled in the study and receive 6 g/day of Ace-ER for 48 weeks.

Subjects will take 4 tablets (500 mg each for 2 g per dose) orally 3 times per day (TID). The dose should be taken with food (i.e. within 30 minutes after a meal or snack). Treatment will be administered for a total of 48 weeks. Study visits will occur every 12 weeks during the Treatment Period during which the scheduled assessments will be administered as outlined in the Schedule of Events (Appendix 10.5).

[figure not shown]
Safety will be evaluated by review of the incidence and frequency of AEs and SAEs, and clinically significant changes in interval history, physical examination results, vital signs, clinical laboratory test results, concomitant medications, and suicidal ideation and behavior (assessed using the Columbia Suicide Severity Rating Scale [C-SSRS]).

Information on biomarkers will be collected to assess their value in predicting clinical severity and disease progression, as well as the ability to determine the long-term impact of disease-targeted treatments and therapies for GNEM.

Efficacy will be evaluated by dynamometry as a measure of muscle strength and patient-reported outcome measures as measures of physical functioning and quality of life.

[Figure 3.1](#) provides a schematic of the study design. The schedule of assessments is shown in Appendix 10.5.

Figure 3.1: Study Schema

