3.3 Blinding and Randomization Methods

This is an open-label study and consists of one treatment arm. All subjects will be treated with Ace-ER 6 g/day. Randomization, blinding and stratification factors are not applicable in this study.

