4.4 Covariate(s)

All models used for each individual clinical endpoint will incorporate the baseline value as a covariate.

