8 STATISTICAL METHODS OF ANALYSES

8.1 General Principles

The statistical analyses will be reported using summary tables, figures, and data listings. Statistical tests, if any, will be 2-sided at the 5% level of significance. All p-values will be presented as nominal p-values. No adjustment on multiplicity will be made. Confidence intervals will be 2-sided 95% confidence intervals, unless stated otherwise. Continuous variables will be summarized by number of subjects and mean, SD / SE, median, minimum, and maximum values. Categorical variables will be summarized by number and percentage. No imputation on missing data will be made, unless stated otherwise.

The final analysis will be conducted when all patients enrolled in the study have completed the Week 48 visit or have discontinued the study.

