8.2 Repeated Measure Model: General Estimating Equations

The efficacy endpoints are collected over time and will be analyzed using a generalized estimation equation (GEE) model that includes time as the categorical variable and adjusted for baseline measurement. The covariance structure that will be used for the GEE model is compound symmetry which specifies constant variance for the assessments and constant covariance between the assessments over time. If the compound symmetry covariance structure leads to non-convergence, Quasi-Likelihood Information Criterion (QIC) will be used to select the best covariance structure. Model based estimates of the changes from baseline and corresponding 95% confidence intervals will also be provided along with p-values for assessing statistical significance.

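### One-arm GEE with baseline as a covariate: the interval for mean change omits the sampling variation of the baseline mean and is too narrow when change depends on baseline

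*SAP*

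**What the plan says.** The design has no comparator. SAP 3.3: "This is an open-label study and consists of one treatment arm". The planned size is about 45 (SAP 3).

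The efficacy model is stated in SAP 8.8: "Changes from baseline will be the dependent variable, and baseline, visit will be the independent variables in the model". SAP 4.4 makes the covariate general: "All models used for each individual clinical endpoint will incorporate the baseline value as a covariate". Protocol 7.6.4 agrees: "Baseline will be included as a covariate in the model". The protocol synopsis says the same.

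SAP 8.2 sets the working structure, "The covariance structure that will be used for the GEE model is compound symmetry", and the inferential output: "Model based estimates of the changes from baseline and corresponding 95% confidence intervals will also be provided along with p-values for assessing statistical significance". Under SAP 8.1, "Statistical tests, if any, will be 2-sided at the 5% level of significance", and p-values are nominal.

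Three things are left open: the baseline value at which the change is evaluated, whether the standard error is sandwich or model-based, and whether the sampling variation of the baseline mean enters the variance. SAP 8.8 also plans descriptive summaries of observed change at each visit, and SAP 8.1 lists SD/SE among the statistics.

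**The concern.** In a randomised comparison, a baseline covariate removes noise from a between-arm difference. Here there is no difference to sharpen. With complete data, the fitted change at the sample mean baseline is simply the raw mean change, so the covariate leaves the estimate where it was. The reported standard error still falls, because it is built from the residual variance after regression on baseline. The part of the variance that comes from having drawn these particular baselines is lost.

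The GEE intervals and p-values for GNEM-FAS and dynamometry are at stake. Where the shortfall matters, it makes change look more certain than it is, in an open-label trial with no control.

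**Working it through.** **Plan's own figure.** The documents give no figure for the precision of a mean change. Their only numerical design claim is at least a 98% chance of one or more drug-related SAEs with 45 subjects at a 10% rate. It reproduces (1 − 0.9^45 = 99.1%) and has no bearing here.

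**Inputs.** From the documents: one arm, n about 45, four post-baseline visits, change regressed on baseline and visit, exchangeable working correlation, two-sided 5%. Assumed: r, the baseline-to-visit correlation, and the ratio of follow-up SD to baseline SD.

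**Formula.** Let D = Y − B be the change and b the slope of D on B.
- Estimate at the sample mean baseline, complete data: mean(D).
- Variance that the model reports: Var(D|B)/n.
- Variance of mean(D) over repeated samples: [Var(D|B) + b² Var(B)]/n.
- Omitted term: b² Var(B)/n.

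**Equal variances s².** Then b = r − 1, Var(D) = 2s²(1 − r) and Var(D|B) = s²(1 − r²). The ratio of reported to true SE is sqrt((1 + r)/2). Coverage is 2Φ(1.96 × ratio) − 1. With s = 1 and n = 45:

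| r | b | true SE = sqrt(2(1−r)/45) | reported SE = sqrt((1−r²)/45) | ratio | coverage |
|---|---|---|---|---|---|
| 0.5 | −0.50 | 0.149 | 0.129 | 0.866 | 91.0% |
| 0.7 | −0.30 | 0.115 | 0.106 | 0.922 | 92.9% |
| 0.9 | −0.10 | 0.067 | 0.065 | 0.975 | 94.4% |
| 0.95 | −0.05 | 0.0471 | 0.0465 | 0.987 | 94.7% |

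**Unequal variances.** Let k be follow-up SD divided by baseline SD. Then b = kr − 1, Var(D|B) = k²(1 − r²) and Var(D) = 1 + k² − 2kr, in units of the baseline variance. At r = 0.9:
- k = 1.1: b = −0.01, ratio sqrt(0.2299/0.23) = 1.00, so no error.
- k = 0.9: b = −0.19, ratio sqrt(0.1539/0.19) = 0.90.

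The slope drives the size, not r alone.

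**Simulation.** 45 subjects, four visits, constant correlation, no true change, exchangeable GEE, sandwich SE, z-test at the last visit, 4,000 trials per setting:

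| r | actual SD of estimate | mean SE, with / without covariate | rejection, with / without |
|---|---|---|---|
| 0.5 | 0.151 | 0.126 / 0.146 | 10.5% / 6.8% |
| 0.7 | 0.116 | 0.104 / 0.114 | 8.7% / 5.9% |
| 0.9 | 0.067 | 0.063 / 0.065 | 6.5% / 5.7% |

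Rejection above 5% without the covariate reflects small-sample z-testing and simulation error, which are separate from this point.

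A second set of 1,500 trials per setting gave these results at r = 0.5:
- The model-based SE falls short in the same way: 0.128 against an actual SD of 0.154.
- Adding the omitted term raises the sandwich SE from 0.126 to 0.146.
- With 20% random dropout the shortfall remains (0.138 against 0.155), but the adjusted estimate no longer equals the raw mean.

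**The case against.** **The interval is valid conditional on the observed baselines.** That is true. But the stated objective concerns patients with severe ambulatory impairment, and the endpoints are changes from baseline, not changes at a fixed baseline value. For the population mean change, the omitted term belongs in the variance.

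**The size may be very small.** This largely stands for strength. The protocol describes slow progression. It also reports a 48-week upper-extremity composite difference of 3.46 kg with p = 0.0031 in UX001-CL201. Assume 40–47 subjects split evenly: t is about 3.1, the SE about 1.1 kg, and the residual SD about 3.5–3.8 kg. With an assumed baseline SD of 8–20 kg, r = sqrt(1 − (residual SD/baseline SD)²) is about 0.88–0.98. The shortfall is then 0.4–3.0%. At an assumed 6 kg it is 5–6%. Those subjects were less impaired and the baseline SD is not in the documents, so this is only indicative. A reader might take 91% coverage, or a doubled false-positive rate, as the expected result. The documents do not support that; r = 0.5 is one end of an assumed range.

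**The raw changes are tabulated anyway.** This stands as mitigation: a reader can form mean ± t × SD/√n. But SAP 8.2 makes the GEE interval and p-value the inferential output.

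**Baseline helps when visits are missing.** This also stands. Apart from the dynamometry rules, efficacy data are not imputed, and deleting the covariate without replacement would discard that information. It is a reason to choose the replacement model carefully.

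**Efficacy is secondary, nominal and unpowered.** That limits the importance. It does not make an interval labelled 95% correct.

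**Conclusion.** The point holds, in a modest form. For GNEM-FAS and dynamometry, the planned GEE interval for the population mean change is too narrow whenever the slope of change on baseline is non-zero. Sandwich errors do not cure it. Under equal variances the SE is about 1–3% too small at r = 0.9–0.95, 8% at 0.7 and 13% at 0.5. With unequal variances it can be larger, smaller or nil. These figures assume evaluation at the sample mean baseline, complete data and the stated r; the documents supply neither r nor an SD.

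Three stronger readings should be resisted.
- **That the estimates of change are biased.** With complete data they equal the raw means; only the stated precision is wrong.
- **That every model in the SAP is affected.** SF-36 and CK are affected only if baseline is a covariate there. SAP 8.9.3 names GEE for CK without saying so, and SAP 4.4 speaks of clinical endpoints. PGI-C has no baseline value of its own, so the point does not apply to it.
- **That every reported interval will be too narrow.** If model-based errors under compound symmetry are used and the variance of change grows over time, a separate pooling error can make early intervals too wide. One simulated case rejected 2.7% at Week 12 and 8.8% at Week 48.

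The primary safety endpoint is untouched.

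**What to change.** In SAP 4.4, 8.2 and 8.8, and in protocol 7.6.4 with its synopsis counterpart, replace the change-on-baseline model. Model the scores themselves, with visit as a five-level factor (Baseline, Weeks 12, 24, 36, 48), and report each visit-minus-Baseline contrast. Specify sandwich standard errors, a small-sample correction and a t reference. This keeps baseline information for subjects with missing visits. Removing the covariate and leaving the SE type unstated would not be enough, because of the compound-symmetry and small-sample effects noted above.

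Alternatively, keep the covariate, state that the change is evaluated at the mean baseline, and add slope² × Var(baseline)/n to the variance. State in SAP 8.9 which approach applies to SF-36 and CK.

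The cost is SAP and protocol wording and one model statement. Intervals become slightly wider and, with missing visits, point estimates shift slightly. Data collection and sample size do not change.

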8.8.1 Dynamometry

Hand held dynamometry testing of multiple muscle groups will be used to measure strength. Test administration at the Screening visit is intended to provide experience and familiarize the subject with the assessments for the evaluator and the subject and data collected will not be used for analysis. The maximum voluntary isometric contraction (MVIC) against a dynamometer will be used to measure bilateral strength in the following muscle groups: shoulder abductors, wrist extensors and knee extensors. Specialized dynamometers for the measurement of grip and key pinch strength will also be used. The total force (in kg) for each will be recorded at the time of test administration. The highest force value collected for each muscle group will be used for data analysis. The percent predicted values will be calculated

after the testing using published normative data (Appendix 10.2). Missing measurements in dynamometry will be handled according to specified rules in the Appendix 10.3.

8.8.2 GNEM-FAS Expanded Version

The original GNEM-FAS was developed as a clinician-reported outcome measure (ClinRo) for ambulatory GNEM patients but has since been modified to include additional items to accommodate weaker patients. This modified version is referred to as the GNEM-FAS Expanded Version and will be used in this study. The scale consists of 3 domains: upper extremity, mobility, and self-care; scores for each domain and a total score will be calculated. Test administration at Screening Visit is intended as practice for the evaluator and the subject, and data collected will not be used for analysis. The GNEM-FAS Expanded Version used in this study is a modified version of the original GNEM-FAS with added questions to accommodate weaker patients. Three items regarding sitting ability were added to mobility domain; one item of picking up small items was added to upper extremity domain; and one item of chewing and swallowing was added to self-care domain.

8.9 Exploratory Analyses

The exploratory endpoints of the study include health related QoLs (SF-36v2, PGI-S and PGI-C) and biomarkers. The exploratory efficacy analyses will be mostly performed in descriptive statistics. Analysis for SF-36v2 can be performed in a similar fashion as described for secondary efficacy analyses if appropriate.

8.9.1 Short Form - 36 Health Survey

The Short Form -36 Health Survey (SF-36v2) version 2 is a validated 36-item questionnaire that yields an 8-domain scale scores and two component summary measures of health-related quality of life. It will be evaluated at Baseline, Week 12, Week 24, Week 36, and Week 48. The domain scales are as follows:

- Physical Functioning (PF): Items 3a, 3b, 3c, 3d, 3e, 3f, 3g, 3h, 3i, 3j .
- Role-Physical (RP): Items 4a, 4b, 4c, 4d.
- Bodily Pain (BP): Items 7, 8.
- General Health (GH): Items 1, 11a, 11b, 11c, 11d.
- Vitality (VT): Items 9a, 9e, 9g, 9i.
- Social Functioning (SF): Items 6, 10.
- Role-Emotional (RE): Items 5a, 5b, 5c.
- Mental Health (MH): Items 9b, 9c, 9d, 9f, 9h

The overall summary measures are as follows:

- Physical Health Component Score (PCS): domain scales PF, RP, BP, GH.
- Mental Health Component Score (MCS): domain scales VT, SF, RE, MH.

Descriptive summary statistics and GEE modeling will be presented for the eight scale scores and PCS and MCS component scores at each time point as well as the change from baseline.

8.9.2 Patient Global Impression of Severity (PGI-S) and Patient Global Impression of Change (PGI-C)

The PGI-S/PGI-C is a self-administered tool widely used in chronic pain clinical trials to indicate the patient's perception about the efficacy of treatment. The PGI-S is conducted at baseline and patient rates the severity of his/her condition on a 7-point categorical scale; the PGI-C is conducted at follow-up visits and a patient rate the change of his/her condition on a 7-point categorical scale. The scales are presented in the table below.

Summary statistics of baseline PGI-S will be reported. The number and percentage of subjects in each category of PGI-S will also be reported. For PGI-C, both summary statistics and GEE estimates will be presented for each time point.

PGI-S	PGI-C
1=Normal, not affected at all	-3=Very much worse
2=Borderline affected	-2=Much worse
3=Mildly affected	-1=Slightly worse
4=Moderately affected	0=No change
5=Markedly affected	+1=Slightly better
6=Severely affected	+2=Much better
7=Extremely affected	+3=Very much better

8.9.3 Biomarkers and Drug Concentration Measurements

Serum Creatine Kinase (CK), serum SA, and urine ManNAc will be collected at baseline, week 12, week 24, week 36, and week 48 or termination visit.

- Free SA: Free SA levels in serum assess the drug concentration in the bloodstream resulting from treatment and are the best indicator of compliance with the treatment regimen. Free SA levels in serum are expressed in micrograms of SA per ml of serum
- Creatine Kinase Levels: CK levels in serum will be measured to assess the degree of reduction of CK levels observed as a surrogate for muscle injury.
- Presence of ManNAc: To detect noncompliance with prohibited medication restrictions during the study period.

The changes from baseline will be summarized and analyzed for the duration of the treatment using GEE.

8.10 Safety Analyses

Adverse event (AE) serves the primary endpoint of the study. Secondary endpoint of Safety Analysis summarizes clinically significant changes from baseline to scheduled time points in:

- Vital signs;
- Concomitant medications;
- Physical examination findings;
- Clinical laboratory evaluations;
- Interval history;
- Suicidal ideation and behavior assessments.

Safety endpoints will be analyzed by using descriptive statistics in the Safety Analysis Set.

8.10.1 Adverse Events

The following AEs will be collected:

- All AEs;
- All SAEs;
- Treatment-related AEs;
- Treatment-related SAEs;
- AEs leading to the discontinuation of study drug or discontinuation of study;
- Deaths.

All AEs recorded from the time the subject signs the informed consent through the safety follow-up will be coded using the Medical Dictionary for Regulatory Activities (MedDRA version 17.1 or beyond).

The number and proportion of subjects with any treatment-emergent adverse events (TEAEs) (defined as any AE occurred after the first dose of study drug) will be summarized by System Organ Class (SOC), Preferred Term (PT), severity, grade, outcome and relationship to treatment for the following types of AEs. Additional summaries of subject incidence (by preferred term) will also be provided.

The severity of AEs will be based on Common Terminology Criteria for Adverse Events (CTCAE), Version 4.03. If an AE cannot be graded based on CTCAE, the investigator will assign a severity based on 1 = mild, 2 = moderate, 3 = severe, 4 = life threatening, and 5 = Death.

For those AEs that occurred more than once during the study, the maximum severity or highest grade will be used to summarize the subject incidence.

Detailed listings for all AEs, serious AEs, AEs leading to the discontinuation of study, and death will also be provided.

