### **7.5.1.5 Safety Follow-up Period**

A Safety Follow-up TC should be initiated by the site personnel 30 (+5) days after a subject's last dose of study drug for subjects who complete the 48-week Treatment Period and choose not to enroll in the extension study, UX001-CL302, or 30 (+5) days after the ET Visit or TC for subjects who discontinue the study early. Information on any ongoing or new AEs, SAEs, and concomitant medications should be collected. Appropriate follow-up of ongoing AE/SAEs should continue until all safety concerns, in the Investigator's opinion, are resolved.

Subjects who have completed the Week 48 Visit of this study, meet the requirements of extension Study UX001-CL302, and choose to enroll in the extension study will not be required to complete the Safety Follow-up TC. However, note that for these subjects, AEs/SAEs should continue to be collected in the parent study until the date of their first dose of study drug in the extension study (see Section [8.5.4](#)).

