4.1 Primary Endpoints

The primary endpoint of the study is the incidence and frequency of AEs and SAEs assessed as related to Ace-ER over the duration of the study.

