7.2 Handling of Missing and Incomplete Data

Missing clinical outcome data can occur for multiple reasons, including missed subject visits and scales or measures with missing item scores. Missing and incomplete data will be identified through a review of tables and listings for this study. Missing and incomplete data will be identified for investigation, and possible resolution, by Data Management prior to the study database lock.

Missing or invalid safety events and assessments will not be imputed or replaced. Missing measurements in HHD individual muscle group test will be imputed as 0 if the reason for missing is due to weakness. When the measurement for one side is missing, the measurement from the other side will be used to impute the missing value. Details of missing observation handling in HHD are provided in Appendix 10.3. Other efficacy endpoints will not be imputed.

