7.2.3 Missing Date Information for Adverse Events and Concomitant Medications

The following conventions will be used to impute missing portions of dates for adverse events and concomitant medications. Note that the imputed values outlined here may not always provide the most conservative date.

Missing Start Dates

- If the day is unknown, then:
 - If the month and year match the first dose of investigational product start date month and year in this study, then impute the day of the first dose date.
 - Otherwise, assign the first day of the month.
- If the month is unknown, then:
 - If the year matches the year of the first dose of investigational product date in this study, then impute the month and day of the first dose date in this study.
 - Otherwise, assign ‘January’
- If the year is unknown, then the date will not be imputed and will be assigned a missing value.

If the imputed date is earlier than birth date, then birth date will be used

Missing Stop Dates

- If the day is unknown, then assign the last day of the month.
- If the month is unknown, then assign ‘December.’
- If the year is unknown, then the date will not be imputed and will be assigned a missing value.
- If the resulting end date is after the date of study completion / discontinuation/ data cutoff, set the imputed end date as the date of study completion / discontinuation/ data cutoff.

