7.2.4 Missing Causal Relationship to Investigational Product for Adverse Events

If the causal relationship to the investigational product is missing for an AE that started on or after the date of the first dose of double-blind investigational product, a causality of “definitely related” will be assigned. The imputed values for causal relationship to investigational product will be used for the incidence summary; the values will be shown as missing in the data listings.

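### As worded, SAP 8.10.1, 7.2.3 and 7.2.4 misclassify AEs with a partial onset date or missing causality in the tables that carry the primary endpoint

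*SAP*

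**What the plan says.** - **Endpoint.** SAP 4.1 makes the primary endpoint the "incidence and frequency of AEs and SAEs assessed as related to Ace-ER over the duration of the study".
- **What is tabulated.** SAP 8.10.1 summarises treatment-emergent AEs, among other things by relationship to treatment. It defines them as "defined as any AE occurred after the first dose of study drug". AEs that are not treatment-emergent appear only in listings.
- **Partial onset dates.** SAP 7.2.3 has two rules that lead to the first-dose date. If the day is unknown and the month and year are those of first dose, "then impute the day of the first dose date". If the month is unknown and the year is that of first dose, "then impute the month and day of the first dose date in this study". Neither rule refers to the AE's stop date.
- **Missing causality.** SAP 7.2.4 assigns the strongest related category when the rating is missing for an AE that "started on or after the date of the first dose of double-blind investigational product". The imputed value goes into the incidence summary.
- **Design.** SAP 3.3 describes one open-label arm and says blinding does not apply.
- **Boundary used elsewhere.** SAP 7.2.4 and SAP 8.10.3 (concomitant medication) both include the first-dose date. Only the treatment-emergent definition says after.
- **Precedence.** Under SAP 1 the SAP overrides the protocol on analysis methods, so its wording governs.

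**The concern.** Three rules decide which AEs enter the related-AE tables, and they do not fit together. One places uncertain onsets on the first-dose date, and another can be read to exclude that date. The date rule can also contradict a stop date that is actually known. The causality rule is meant to count an unrated AE as related, but it is tied to a dose that no subject receives.

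The primary endpoint is a descriptive count of related events in about 45 subjects, so classification rules are most of its analysis. If they are left open, whoever programs the tables decides which events count, possibly with the data in view.

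**Working it through.** **1. The plan's own figure.** SAP 3.4 assumes a 10% true rate of related SAEs with N = 45 and states at least 98% probability of observing one or more. Exact binomial: 1 − 0.9^45 = 0.9913. The figure is reproduced, and nothing below changes it.

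**2. Boundary.** Let F be the first-dose date and A the AE onset date. When either rule in SAP 7.2.3 sends a partial date to first dose, A = F.
- Strict comparison, A > F: false, so the AE is not treatment-emergent.
- Inclusive comparison, A ≥ F: true, so it is.

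An imputed date carries no time of day, so reading after by the clock cannot settle the case. Take one AE with A = F and no causality rating, and read the product in SAP 7.2.4 as Ace-ER. SAP 7.2.4 makes the AE related. SAP 8.10.1, by strict date, then leaves it out of the table by relationship. A medication started on the same day is concomitant under SAP 8.10.3.

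**3. Reach of the date rules.** The documents do not say how many dates are partial. As an assumption, take first-dose dates uniform over a 366-day year and onsets uniform over 48 weeks (336 days). There are 366 × 336 = 122,976 equally likely pairs of first-dose date and onset date.
- Same month as first dose: the sum of L(L+1)/2 over month lengths L is 7 × 496 + 4 × 465 + 435 = 5,767. 5,767 / 122,976 = 4.7%.
- Same calendar year as first dose: 336 × 337 / 2 + 30 × 336 = 66,696. 66,696 / 122,976 = 54%.

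Under these assumptions the day-unknown rule reaches few on-treatment AEs. An on-treatment AE with only the year known would be moved to F about half the time.

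**4. Stop date.** Protocol 7.5.2.10 records AEs from consent, and the Schedule of Events allows screening up to 28 days before Baseline, so AEs from before dosing are in the database. Example: first dose 20 March, AE onset in March with day unknown, AE known to have stopped on 10 March. SAP 7.2.3 gives an onset of 20 March, ten days after the AE ended. Under a strict boundary this AE stays out of the treatment-emergent tables. Once the boundary is made inclusive it enters them. Correcting step 2 alone would therefore expose this gap.

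**5. Causality trigger.** SAP 7.2.4 requires onset from the first dose of a double-blind product. SAP 3.3 rules such a product out. Read literally, no AE meets the condition, and an AE with a missing rating is never counted as related.

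**6. Size per subject.** With the planned 45 subjects: 1/45 = 2.2 percentage points, 2/45 = 4.4, 3/45 = 6.7. The number of subjects affected cannot be derived from the documents.

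**The case against.** The best defence is that the intent is easy to infer. Imputing to first dose, and including that date in two other sections, suggests that such events are meant to count. The double-blind wording looks carried over from another plan. Protocol 8.5.4.1 requires a relationship rating for every AE, and queries are resolved before lock, so missing ratings should be rare. SAP 7.2.3 itself warns "Note that the imputed values outlined here may not always provide the most conservative date". The safety analysis is descriptive, and SAP 8.10.1 lists every AE, so nothing disappears from the report. All of this stands and lowers the severity. It does not make the rules right as written, and the caveat in SAP 7.2.3 does not excuse an onset later than a known stop.

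Some stronger readings are tempting, but the documents do not support them:
- **True Day 1 events are lost.** SAP 8.10.1 refers to the dose, not to its date. Protocol 7.5.1.2 requires Baseline assessments to be completed before dosing. An event that follows the first tablet on Day 1 is already after the first dose. The fault concerns onsets that are known only by date.
- **SAP 7.2 contradicts SAP 7.2.4.** SAP 7.2 says "Missing or invalid safety events and assessments will not be imputed or replaced", but SAP 8.1 allows imputation where the plan states it, and SAP 7.2.4 does so. That largely resolves the tension.
- **The treatment-emergent period has no end and needs a cut-off.** Collection ends at the Safety Follow-up call or first extension dose (Protocol 7.5.2.10). For early terminators that call comes "30 (+5) days after the ET Visit or TC for subjects who discontinue the study early", so off-drug follow-up differs between subjects. A fixed cut-off would nevertheless move related events from tables to listings, although the endpoint covers the whole study.
- **A related SAE could vanish from the primary result.** That would need an SAE with a partial onset date or no causality rating. SAEs are notified within 24 hours (Protocol 8.5.4.2), so this is possible but not likely.

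**Conclusion.** The plan is wrong as written on three linked points, with minor to moderate severity: the first-dose boundary for imputed onsets, the missing stop-date check, and the causality trigger.

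Applied literally, the boundary and the trigger each remove events from the related-AE counts. The stop-date gap works the other way once the boundary is corrected, because it adds events that ended before dosing. A reader should therefore not infer a bias in one known direction across all the rules.

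The size is 2.2 percentage points of incidence per reclassified subject, taking the planned 45 as denominator. The total is unknown, because the documents give no count of partial onset dates or missing ratings. The 4.7% and 54% shares rest on uniform dosing and onset dates and describe how far the date rules reach, not how large the error is. Alpha, power and sample size are untouched.

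**What to change.** Make three edits to the SAP, together and before database lock:

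1. **SAP 8.10.1:** define a treatment-emergent AE as one with onset on or after the first-dose date of study drug.
2. **SAP 7.2.3:** add to both rules that impute to first dose the condition *unless the known stop date is before first dose*. The existing fallback (first day of the month, or January) then applies. In the example above it gives 1 March, which is consistent with a stop on 10 March.
3. **SAP 7.2.4:** replace the double-blind product with study drug (Ace-ER).

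The cost is a few words of text and small changes to the table programs. No new data are needed, and neither trial conduct nor sample size changes. The first two edits should not be separated, because the first without the second would bring some AEs that ended before dosing into the treatment-emergent tables.
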